## 12.0 Provisions to Monitor the Data to Ensure the Safety of Subjects

A Data Safety Monitoring Board (DSMB) will oversee the experiments in Aim 3 (a small-scale randomized controlled trial). This board will consist of a neurologist, a statistician,

and an experienced rehabilitation researcher (all with no direct ties to this study). On a quarterly basis, the DSMB will review the status of the study. The role of the DSMB will be to:

- Protect the safety of study participants
- Review the research protocol, informed consent documents, amendments, and plans for data safety and monitoring
- Evaluate the progress of the trial, including periodic assessments of data quality and timeliness, recruitment, accrual, and retention, participant risk vs. benefit, and other factors that may potentially affect study outcome
- Review study performance, make recommendations and assist in the resolution of problems reported by the Principal Investigator
- Report to the IRB on the safety and progress of the trial
- Ensure the confidentiality of the study data and the results of the monitoring
- Advise the IRB and the study investigators as to whether the protocol should continue as scheduled or undergo a modification due to a finding from the monitoring process

Any adverse events will be recorded, monitored, and promptly reported to the IRB, following policy HRPP 4.7. Our exclusion criteria will minimize the risk of enrolling participants with severe cardiovascular risk. Scheduled rest breaks will be provided between trials during experimental testing, as well as whenever requested. Minimization of risk of adverse events will be accomplished by monitoring vital signs during trials in which subjects are performing potentially demanding exercise. Collected data and any events potentially affecting participant safety will be reviewed by the principal investigator after each data collection session.

## **13.0 Withdrawal of Subjects**

Participants will be withdrawn from the study without their consent if study staff determine that the participants are at risk of negative health events (e.g. large increase in blood pressure from the initial screening assessment; consistent inability to maintain balance while walking on the treadmill). If a participant voluntarily withdraws from the study, their results will not be included in our data analysis, as our intervention sample size accounts for 20% dropout.

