**2.0 Background**

Chronic stroke survivors often experience gait instability, which can reduce quality of life through an increased fall-risk and fear of falling [1-5]. Unfortunately, recent clinical trials focused on strengthening and balance [6], multifactorial fall prevention [7], and locomotor training [8] have all failed to substantially impact this important problem, likely because they were not targeted to the specific mechanisms underlying post-stroke instability. To overcome this obstacle, we must design interventions based on a mechanistic understanding of gait instability, which can ultimately be accessed by patients outside of cutting-edge research laboratories

As it is unlikely that a single intervention will “cure” post-stroke gait instability, our long-term goal is to develop a toolbox of interventions, from which clinicians can select the most appropriate option for individual patients. Toward this goal, this study will investigate the real-time augmentation of hip proprioceptive feedback during post-stroke walking. Essentially, sensory stimulation will augment perceived movement errors, a direct extension of methods promoting useful gait adaptation by mechanically augmenting movement errors [9-10].

This proposal is based on our prior work revealing a sensorimotor strategy of sensing the body’s mechanical state using hip proprioceptive feedback [11] and actively adjusting foot placement in response [12]. This strategy is often disrupted in chronic stroke survivors with poor balance [13]. Our ongoing work indicates that deficits in this stabilization strategy can be improved through mechanical error-augmentation. Here, we will test

whether sensory error-augmentation has similar beneficial effects, while investigating the underlying mechanism and determining whether sensory augmentation should be personalized to individual patients.

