### 3.0 Intervention to be studied

In this study, Aims 1 and 2 do not involve an intervention, instead including cross-sectional mechanistic experiments. Aim 3 will test the safety, feasibility, and efficacy of a novel intervention involving low-intensity vibration applied over the bilateral hip abductor muscles of chronic stroke survivors during walking. This Aim will take the form of an early-stage, small-scale (n=44 participants) randomized controlled clinical trial.

The precise intervention to be studied is novel, as the vibration amplitude applied during walking will be directly controlled by the user's walking mechanics, allowing us to augment the sensory information available to users. However, the method and form of the vibration itself is not novel. Many prior studies have used vibrating motors (as in the present study) to deliver the same type of mechanical vibration to clinical populations during the performance of functional movement tasks (e.g. reaching, standing, walking) [14-17]. We ourselves have published work investigating the effects of mechanical vibration [11, 18-19], and have an IRB-approved project that involves these methods (Pro00046775).

No medication is involved in the intervention, and FDA approval will not be required for the use of our vibrating tactors, which deliver minimal mechanical energy to users – instead simply evoking a sensory response.

The rationale for the intervention is to use non-invasive methods (vibration) to improve the sensory accuracy of chronic stroke survivors. This low-risk method could have the potential to produce large improvements in patient functional mobility. While we have observed no adverse events in the use of these methods, and no such adverse events have been reported in the literature due to the use of these methods, one of the goals of this project will be to definitively establish the safety of this intervention.

For the intervention, the control group will receive vibration applied over the bilateral hip abductors, just as the experimental group. However, the vibration will not be linked to the user's mechanics, instead being randomly delivered – a method that has been used previously [11].

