### 4.0 Study Endpoints

For the intervention in Aim 3, our outcome measure of safety will be the proportion of participants who experience an adverse event potentially related to the intervention (e.g. skin irritation; falls) or any serious adverse event (e.g. hospitalization; death). Our primary measures of feasibility will be participant adherence (percentage of training sessions attended) and drop-out (non-attendance of final assessment session). We will also track the total walking time across training sessions (of a maximum possible 312 minutes). Our primary measure of efficacy will be changes in  $\rho_{\text{disp}}$ , a metric that quantifies the extent to which participants effectively stabilize their gait by adjusting their step width to account for pelvis dynamics [20]. Our secondary measures of efficacy will be the common clinical measures of Functional Gait Assessment score, Activities-specific Balance Confidence score, overground gait speed, and fear of falling.

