### Inclusion Criteria

- Age  $\geq$  21 years
- Experience of a stroke  $\geq$  6 months prior to participation
- Gait speed of at least 0.2 m/s
- Ability to walk on a treadmill without a cane or walker
- Provision of informed consent

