## 9.0 Consent Process

Informed consent will be obtained from participants prior to participation, using a VA Informed Consent form approved by the MUSC IRB. Participants will first be informed of the purpose of the experiments and possible risks. A member of the study staff will then review the Informed Consent form with the potential participant, ensuring they are given adequate time to review the document. The potential participant will be asked if they have any questions about the study, and asked if they agree to participate. The Informed Consent form will be signed by the participant. Copies of the signed forms will be given to the participant. The consent process will take place in a private room in the MUSC College of Health Professions Building. There will be no set period between informing the prospective participant and obtaining the consent. Participants will be reminded that they may end their participation in the study at any point.

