## 10.0 Study Design / Methods

A total of 120 chronic stroke survivors will be recruited for an initial Screening session to determine eligibility for enrollment in the subsequent Aims. From this initial session, 40 stroke survivors will be recruited for Aim 1, and a separate 40 stroke survivors will be recruited for Aim 2. From these 80 participants in Aims 1 and 2, a total of 44 will be recruited for Aim 3. Aim 1 involves a single-session experiment, Aim 2 involves two experimental sessions, while Aim 3 involves an intervention with a total of 10-11 sessions. Participants will be enrolled in this study for a period of a year, allowing time to complete all potential sessions.

In the initial Screening session, participants will walk on an instrumented treadmill for 2-minutes. We will calculate  $\rho_{\text{disp}}$  (a measure of the typical gait stabilization strategy) using LED markers and inertial measurement units placed over participants' legs and pelvis. If  $\rho_{\text{disp}}$  is less than 0.56 (well below control norms), participants will qualify to progress to the subsequent Aims. During the Screening session, we will also quantify the secondary

measures of: Functional Gait Assessment; Activities-specific Balance Confidence scale, Fugl-Meyer Lower Extremity Motor Function subscale; Fugl-Meyer Lower Extremity Sensation subscale; self-selected and fastest-comfortable overground gait speed; fear of falling; fall history. All of these secondary measures are commonly used in clinical practice.

In Aim 1, participants will complete a single-session experiment. We will quantify the cutaneous detection threshold for vibration delivered over the bilateral hip abductors. We will also calculate the lateral sway evoked by vibration of each leg, quantified as the shift in center of pressure while standing on a force plate. Participants will then perform a series of treadmill walking trials. In some of these trials, vibration will be applied to the hip abductors or lateral trunk, while we quantify  $\rho_{\text{disp}}$ .

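### Section 13 turns a staff safety stop into withdrawal from the whole study, so an Aim 3 participant stopped in training has no post-assessment ρ_disp even where a safe assessment was possible (minor, cheap to fix)

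*Combined protocol and SAP*

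**What the plan says.** Section 13.0 (Withdrawal of Subjects) sets the rule: "Participants will be withdrawn from the study without their consent if study staff determine that the participants are at risk of negative health events". It names two example triggers: a large rise in blood pressure since screening, and "consistent inability to maintain balance while walking on the treadmill". The sentence on leaving results out of the analysis covers voluntary withdrawal only; how staff-withdrawn participants are analysed is not stated.

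Section 10.0 (Study Design / Methods) places the Aim 3 outcome measures, including ρ_disp, in the first and last sessions. Section 11.0 (Data Management) makes the primary Aim 3 analysis an independent t-test on the change in paretic ρ_disp and gives no method for missing values. Section 4.0 (Study Endpoints) counts anyone who does not attend the final assessment as a drop-out. No section provides for an assessment after a staff stop.

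**The concern.** Stopping the training and ending follow-up are different decisions, and Section 13.0 makes them one. Someone unfit for repeated training sessions may still be fit for a short harnessed walk, or at least for questionnaires. A blood pressure rise, for example, could settle before the final session. Under the rule as written, that participant's outcome is lost after randomisation.

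The loss may also be informative. Section 2.0 says of the gait stabilisation strategy: "This strategy is often disrupted in chronic stroke survivors with poor balance". The balance trigger is therefore related to the construct that ρ_disp measures. That sentence concerns the level of the strategy, however, and not its change with training, so the strength of the link is unknown.

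At stake are a few randomised outcomes in a 44-person trial. The treatment contrast is biased only if stops are related to the change in ρ_disp and the stop process also differs between arms.

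**Working it through.** **1. The plan's own figures.** Section 11.0 gives an effect size of 1.0, alpha 0.05, power 0.80, 17 per group, and 22 per group after 20% dropout. A two-sided two-sample t-test (noncentral t) needs n = 16.71, rounded up to 17, with power 0.807 at 17. Then 17 / 0.8 = 21.25, rounded up to 22. Both figures reproduce. Power is 0.900 with all 22 per group and 0.885 with 20 v 22. A few stops therefore cost little power, and what remains to check is bias.

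**2. What follows from the text.** A stop is withdrawal from the study (Section 13.0). The post value comes only from the last session (Section 10.0), and the t-test needs it (Section 11.0). A participant who has been withdrawn attends no last session, so there is no change score.

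**3. Size of a possible bias.** The documents give no stop rates, correlations or arm differences, so all of these are assumptions. The calculation works in SD units of the change score, with 22 per arm and no true effect. A stop variable W has correlation r with the change, and a participant is stopped if W falls below its p-quantile c. The mean change among those remaining rises by r·φ(c)/(1 − p):

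- p = 1/22 = 0.0455: φ(c)/(1 − p) = 0.0956/0.9545 = 0.100
- p = 2/22 = 0.091: φ(c)/(1 − p) = 0.1636/0.909 = 0.180

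The shift in the contrast is r times the difference between arms. For 9% v 4.5% this is r × (0.180 − 0.100) = 0.024 / 0.040 / 0.080 at r = 0.3 / 0.5 / 1.0. The table adds type I error from simulation (100,000 trials per cell, nominal 0.05):

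| Stop rates | Shift in SD, r = 0.3 / 0.5 / 1.0 | Type I error |
|---|---|---|
| Equal (4.5% or 9% in both arms) | 0.00 | 0.050–0.051 |
| 9% v 4.5% | 0.02 / 0.04 / 0.08 | 0.051 / 0.051 / 0.059 |
| 4.5% v 0 | 0.03 / 0.05 / 0.10 | 0.052 / 0.053 / 0.060 |
| 9% v 0 (upper case, about 2 v 0 of 22) | 0.05 / 0.09 / 0.18 | 0.053 / 0.060 / 0.089 |

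For comparison, the standard error of the contrast is √(2/22) = 0.30 SD and the design effect is 1.0 SD.

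**4. Chance imbalance is not bias.** With equal true rates, the two arms' stop counts differ by 2 or more in 25% of trials (p = 0.0455) and 42% (p = 0.091). The expected shift is still zero.

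**5. What the fix recovers.** At 9% v 4.5%, if a random half of those stopped are re-measured, the shift falls to 0.01 / 0.02 / 0.04 SD. If only the less affected half return, it is 0.01 / 0.02 / 0.05 SD. The bias is reduced, not removed.

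**6. What the fix costs in power.** Suppose 2 of 22 Augmented participants are stopped and gain nothing, and 1 of them is re-measured. The expected effect becomes 20 × 1.0 / 21 = 0.95 SD and power (21 v 22) is 0.86. Leaving both out gives 0.89 (20 v 22 at 1.0 SD).

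**The case against.** The strongest objection is that the remedy works least well where it is most needed. The trigger that makes the missing values informative is imbalance on the treadmill, and the documents describe ρ_disp only from treadmill walking. Those participants are the least likely to be assessed safely. For the blood pressure trigger, where re-measurement is more plausible, no link with the change in ρ_disp has been argued. This stands, and it limits the benefit for the primary outcome. It does not apply to balance confidence and fear of falling, which need no walking.

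Stops should also be rare. Entry requires "Ability to walk on a treadmill without a cane or walker", and every Aim 3 participant has already walked on the treadmill at screening and in an earlier Aim: "From these 80 participants in Aims 1 and 2, a total of 44 will be recruited for Aim 3". Training is at self-selected speed in a harness. The arms are physically similar: "the control group will receive vibration applied over the bilateral hip abductors, just as the experimental group". The documents neither show nor exclude a difference in stops by arm. The numbers lost are covered by the 20% allowance, and the data safety monitoring board reviews retention quarterly. All of this is fair and is why the point is minor. The allowance, however, protects power and does nothing about informative loss.

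Section 13.0 does not forbid an assessment before the withdrawal takes effect. That is true, but nothing provides for one, so whether it happens is left to chance.

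Finally, a stopped participant who attends the last session would no longer count as a drop-out under Section 4.0, which lowers that feasibility measure. This also stands, and staff stops therefore need to be reported separately.

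**Conclusion.** The concern holds, as a minor point. Read as written, Section 13.0 gives up post-assessment data from randomised participants that could sometimes be obtained safely. That no post value would exist is an inference, but a direct one from Sections 10.0, 11.0 and 13.0 taken together.

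Any bias is likely to be small against the standard error: zero with equal rates and the same stop process in both arms, and well under 0.1 SD in the more plausible unequal cases. Type I error clearly exceeds 0.06 in only one cell of the table, where stops fall in one arm alone at 9% and depend entirely on the outcome. These figures rest on assumed stop rates and correlations. The planned sample size is unaffected.

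**What to change.** Keep the stopping criteria in Section 13.0 and add the following for Aim 3:

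- A staff stop ends training, not study participation. The participant stays in the assigned arm.
- The participant is invited to the planned final session and may decline, in keeping with Section 9.0: "Participants will be reminded that they may end their participation in the study at any point".
- At that session the participant completes the Activities-specific Balance Confidence scale and the fear-of-falling measure. The walking measures, including ρ_disp in the harness, are done only if staff judge them safe.
- Any ρ_disp obtained enters the primary analysis in the assigned arm.
- Staff stops are reported by arm and reason alongside all-cause drop-out, whose definition in Section 4.0 stays as it is.

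The cost is some protocol and consent wording and a few visits, using a session already planned. Some participants stopped for treadmill imbalance will still lack ρ_disp. Including partly trained participants can dilute a true effect slightly, as the power example in step 6 shows.

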## 11.0 Data Management

For Aim 1, our first analysis will be correlation-based, testing whether metrics of altered perception or cutaneous cueing are associated with the beneficial effects of sensory augmentation. For each participant, we will quantify four independent variables: cutaneous detection threshold (paretic and non-paretic legs); lateral sway distance evoked by hip abductor vibration (paretic and non-paretic legs). We will also quantify the effect of sensory augmentation during gait as the mean change in paretic  $\rho_{\text{disp}}$  between the Normal and Vibrated Abductors trials ( $\Delta \rho_{\text{disp}}$ ). We will test whether each of the four independent

variables is significantly associated with  $\Delta \rho_{\text{disp}}$ , using an alpha value of 0.0125 to account for multiple comparisons. Our second analysis will involve a repeated measures experimental design – directly testing whether vibration designed solely to provide cutaneous cues (Vibrated Trunk condition) has a smaller beneficial effect than vibration designed to elicit both cutaneous cues and an altered perception of pelvis mechanics (Vibrated Abductors condition). For this analysis, we will use a repeated measures ANOVA to compare mean paretic  $\rho_{\text{disp}}$  values during the Normal, Vibrated Abductors, and Vibrated Trunk trials.

For Aim 2, our primary statistical analysis will compare the average increase in paretic  $\rho_{\text{disp}}$  values during Standard Augmentation and Personalized Augmentation conditions (relative to Normal). We will use a paired t-test to compare these  $\Delta \rho_{\text{disp}}$  values. Secondarily, we will use a repeated measures ANOVA to test for group-wide effects of vibration pattern and location, based on data from the first session.

For Aim 3, our primary statistical analysis will use an independent t-test to determine whether the change in paretic  $\rho_{\text{disp}}$  differs significantly between the Augmented and Control groups.

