Power analyses were performed for each Aim. For Aim 1, the proposed sample size (n=40) was selected to be able to detect a moderate correlation ( $r=0.5$ ) between our input variables and  $\Delta \rho_{\text{disp}}$ . Aim 2 was powered to detect a moderate effect size (Cohen's  $d = 0.5$ ) between Standard and Personalized sensory augmentation methods. For our Aim 3 intervention, we estimate an effect size of 1.0 based on our prior results. It should be noted that we expect this effect to increase with the repeated exposure to sensory augmentation proposed here. With an effect size of 1.0 and an alpha value of 0.05, we will need 17 participants per group for 0.80 power. We propose 22 participants per group to account for 20% dropout.

Steps will be taken to minimize the risk of loss of confidentiality. All data will be stored on a password-protected computer and password-protected secure server that is backed-up nightly.

The RESTORE registry (Pro#00037803), from which this study will recruit subjects, also serves as a data analysis tool by which interdisciplinary teams may share data across projects and provide MUSC's stroke recovery research community with a more complete registry with key stroke elements. Some subjects may have participated or will participate in other stroke related research studies at MUSC. Sharing data from this and other stroke research studies with RESTORE will allow for more targeted recruitment efforts in the future and could reduce the burden placed on subjects by reducing the duplicative efforts of collecting common data and physical function assessments requested by multiple studies and storing them in one centralized and secure location.

Subjects are informed in the consent process if they enroll into the RESTORE registry, their data from this study will be shared. Subjects will be asked to sign a HIPAA authorization stating their health information may be disclosed to MUSC investigators requiring their data for their research projects upon approval by an Institutional Review Board.

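### Section 13 removes voluntary withdrawers from the analysis, although Section 4 makes drop-out, adherence and adverse events Aim 3 outcomes; a power allowance is the only reason given

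*Combined protocol and SAP*

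**What the plan says.** Section 13.0 (Withdrawal of Subjects) sets the rule: "If a participant voluntarily withdraws from the study, their results will not be included in our data analysis". Its reason follows in the same sentence: "as our intervention sample size accounts for 20% dropout". The wording names no aim, but the reference to the intervention's sample size ties it to Aim 3. It applies to voluntary withdrawal only. The section does not say how data are handled for participants withdrawn by staff.

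Section 4.0 (Study Endpoints) defines the Aim 3 outcomes. For feasibility: "Our primary measures of feasibility will be participant adherence (percentage of training sessions attended) and drop-out (non-attendance of final assessment session". For safety: "our outcome measure of safety will be the proportion of participants who experience an adverse event potentially related to the intervention", or any serious adverse event. Total walking time is also tracked.

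Section 3.0 raises the stakes on safety: "one of the goals of this project will be to definitively establish the safety of this intervention".

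Section 11.0 (Data Management) gives the efficacy test: "For Aim 3, our primary statistical analysis will use an independent t-test to determine whether the change in paretic" ρ_disp differs between arms. It raises 17 evaluable participants per group to 22: "We propose 22 participants per group to account for 20% dropout".

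Section 12.0 covers monitoring: "Any adverse events will be recorded, monitored, and promptly reported to the IRB". It also has the DSMB look at retention each quarter.

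No section defines an analysis set, a safety population or a method for missing data, and none exempts the Section 4 outcomes from the Section 13 rule.

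**The concern.** Inflating the sample size for dropout answers one question: will enough participants remain for adequate power? It does not answer whether those who remain represent those who were randomised, and it is no reason to discard data already collected.

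The rule also removes the people whom some outcomes are meant to describe. Drop-out counts participants who miss the final visit, and voluntary withdrawers will be among them. Their low attendance belongs in adherence. Any skin irritation or fall they had belongs in the safety proportion. Aim 3 exists to establish safety, feasibility and efficacy, so a rule that flatters the first two weakens the trial's main product. For efficacy, removing participants after randomisation for a reason that may relate to outcome can bias the comparison between arms.

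**Working it through.** **1. The plan's own figure.** Two-sample t-test, d = 1.0, α = 0.05 (taken as two-sided; the plan does not say), power 0.80. The noncentral-t solution is 16.71, so 17 per group, with power 0.807. Inflation: 17 / (1 − 0.20) = 21.25, so 22 per group and 44 in total. The sample size reproduces and is not in dispute.

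**2. Drop-out.** Take 9 of 44 lost (20% of 44 = 8.8). If v of the 9 are voluntary and are excluded, the reported rate is (9 − v) / (44 − v). The values of v are assumptions; intervals are exact (Clopper-Pearson) 95%.

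| Case | Drop-out |
|---|---|
| All randomised | 9/44 = 20.5% (9.8–35.3) |
| v = 9 | 0/35 = 0% (0–10.0) |
| v = 6 | 3/38 = 7.9% (1.7–21.4) |
| v = 3 | 6/41 = 14.6% (5.6–29.2) |

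Removing a drop-out takes one from numerator and denominator, so the reported rate always falls. It reaches zero only if every drop-out withdrew voluntarily.

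**3. Adherence.** Section 10 gives 10–11 sessions. Taking off the pre- and post-assessments and the optional personalisation session leaves 8 training sessions. Assume completers attend 7.5 of 8 on average and drop-outs 3 of 8.

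- All 44: (35 × 7.5 + 9 × 3) / (44 × 8) = 289.5/352 = 82.2%
- v = 9: 262.5/280 = 93.8%
- v = 6: 271.5/304 = 89.3%
- v = 3: 280.5/328 = 85.5%

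**4. Safety.** Assume 6 of 44 have a qualifying event, 3 of them among 9 voluntary withdrawers. The true proportion is 6/44 = 13.6% (5.2–27.4); the reported one is 3/35 = 8.6% (1.8–23.1). The number of events can only fall. The proportion falls only if withdrawers have a higher event rate than the rest, as assumed here.

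**5. Efficacy.** Simulation, 100,000 trials per scenario: 22 per arm, unit-variance normal change scores, no true effect, and 4 per arm withdrawing (20% of 22 = 4.4). Withdrawal propensity correlates with poor outcome at 0.5, 0.7 or 1.0, either in one arm (random in the other) or in both. Correlation 1.0 is an extreme. When withdrawal is unrelated to outcome, type I error is 4.97%.

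| Scenario | Bias in SD (0.5 / 0.7 / 1.0) | Type I error (0.5 / 0.7 / 1.0) |
|---|---|---|
| One arm, all 4 absent | 0.15 / 0.22 / 0.31 | 7.9 / 10.9 / 18.7% |
| One arm, 2 of 4 analysed | 0.07 / 0.10 / 0.14 | 5.6 / 6.3 / 7.8% |
| Both arms, all 4 absent | none | 5.8 / 6.7 / 9.6% |
| Both arms, 2 of 4 analysed | none | 5.1 / 5.4 / 6.1% |

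At a weaker correlation of 0.3 in one arm, the bias is 0.09 SD and type I error 6.0%. If all 4 withdrawers attend the final assessment and are analysed, type I error returns to about 5%.

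**The case against.** The strongest reply is that the rule was meant for efficacy only. Its reason is the power allowance, the only Aim 3 test in Section 11 is the t-test, and counting an absence does not need the absentee's results. On that reading drop-out is untouched, and the text needs clarifying, not correcting. This is a fair guess at intent, but the sentence is unqualified and nothing elsewhere limits it. Even read that way, it removes any withdrawer who has, or would agree to give, a post-assessment from a randomised comparison.

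Second, adverse events are still recorded and reported, and the DSMB sees retention. This stands for monitoring: participant protection is not lost. But Section 12 does not say that these events count in the Section 4 proportion.

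Third, someone who leaves the study usually has no post-assessment, so the t-test would lose them with or without the rule. This largely stands. The rule itself accounts only for withdrawers who could have been analysed. In the one-arm simulation, if 2 of 4 could be, that is the step from 0.15 to 0.07 SD at correlation 0.5. The one-arm pattern also needs withdrawal to work differently by arm, although both arms receive vibration at the same site. Similar withdrawal in both arms is at least as plausible and gives no mean bias.

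Fourth, the safety contrast and all withdrawal patterns are assumed. They are, because the documents give only the 20% allowance.

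**Conclusion.** The concern holds. Sections 4 and 13 conflict as written, and the stated justification does not support the exclusion. This conclusion rests on the text alone and is secure. It must be fixed, because a primary feasibility measure cannot be computed as defined while the Section 13 sentence stands.

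The size of the distortion depends on assumptions about how many withdraw and why. Drop-out is always understated once a voluntary withdrawer has missed the final visit. Adherence is overstated if withdrawers attended less than the rest. The safety proportion shifts according to withdrawers' event rate. The efficacy consequence is the least certain: modest at correlations of 0.3 to 0.5, serious only when withdrawal is strongly tied to outcome in one arm, and due in large part to missing assessments. The rule does not touch staff-initiated withdrawals, no-shows, or participants who miss training but attend the final session.

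**What to change.** Replace the exclusion sentence in Section 13 with provisions to this effect:

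1. Data collected up to withdrawal are kept and analysed. The consent pages were not available for this review, so check this against the consent terms.
2. Safety, adherence, walking time and drop-out are computed on all 44 randomised participants by assigned group, whether they left voluntarily, were withdrawn by staff or did not attend.
3. Participants who stop training are invited, if they agree, to the final assessment already planned. Efficacy is analysed by assigned group on everyone with a post-assessment.
4. One sensitivity analysis addresses missing post-assessments, with a statement that a missing-at-random method will not remove bias from outcome-dependent dropout.

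Report withdrawals by arm, type and reason. Keep the 20% allowance as a statement about power only. Items 1 and 2 resolve the conflict with Section 4. Items 3 and 4 address the efficacy comparison, which deleting the sentence alone would not repair.

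The cost is a few sentences of protocol text, one extra analysis and staff time for invitations. It needs no additional participants and no new type of visit.
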